#### **4.3.5. Change in Work Productivity and Activity Impairment – Migraine (WPAI-M) Scores from Baseline to Each 4-Week Treatment Period**

##### **4.3.5.1. Definition of Endpoint**

The Work Productivity and Activity Impairment-Migraine (WPAI-M) is a 6-item self-administered questionnaire that measures work productivity and the amount of time missed from work due to migraine. Scores are based on a percentage, so the range of scores is 0-100%, with higher scores indicating greater impairment and less productivity.

#### **4.3.5.2. Main Analytical Approach**

See Appendix 6.3.3 for WPAI-M scoring information. Only data from those participants who meet criteria for the Full Analysis set will be analyzed. Data for this secondary endpoint will be analyzed via a repeated measures ANOVA comparing changes in participant's total WPAI-M scores from baseline (Visit 2) to each of the 4-week treatment periods (Visit 3, 4, and 5). Significant changes will be followed up using within groups, repeated measures *t*-tests as needed.

#### **4.3.6. Change in Neuro-QoL Sleep Disturbance Short Form (SDSF) Scores from Baseline to Each 4-Week Treatment Period**

##### **4.3.6.1. Definition of Endpoint**

The Neuro-QoL Sleep Disturbance Short Form (SDSF) is an 8-item, self-administered questionnaire which measures quality of sleep including difficulties and perception of sleep satisfaction. Possible scores range from 8 to 40, with higher scores indicating worse sleep habits.

##### **4.3.6.2. Main Analytical Approach**

See Appendix 6.3.4 for SDSF scoring information. The variable used to measure the secondary efficacy endpoint of change in Neuro-QoL Sleep Disturbance Short Form (SDSF) between treatment month scores will be calculated using the scales online scoring service (<https://www.assessmentcenter.net>). By using the online scoring service participants raw scores for this endpoint will be calculated into T-Scores which will allow for a standardized comparison between the treatment months. Only data from those participants who meet criteria for the Full Analysis set will be analyzed. Data for this secondary endpoint will be analyzed via a repeated measures ANOVA, comparing mean changes in participant's total SDSF scores from baseline (Visit 2) to each of the 4-week treatment periods (Visit 3, 4, and 5). Significant changes will be followed up using within groups, repeated measures *t*-tests as needed.

#### **4.3.7. Change in General Self-Efficacy Short Form 4a (GSE-SF) Scores from Baseline to Each 4-Week Treatment Period**

##### **4.3.7.1. Definition of Endpoint**

The General Self-Efficacy Short Form 4a (GSE-SF) is a 4-item, self-administered questionnaire where the participant is asked to rate their confidence in managing situations, problems, and events. Scores range from 4-20. Higher scores indicate the participant has more self-efficacy managing difficult situations.

#### **4.3.7.2. Main Analytical Approach**

See Appendix 6.3.5 for GSE-SF scoring information. The variable used to measure GSE-SF between treatment month scores will be calculated using the scales online scoring service (<https://www.assessmentcenter.net>). By using the online scoring service participants raw scores for this endpoint will be calculated into T-Scores which will allow for a standardized comparison between the treatment months). Only data from those participants who meet criteria for the Full Analysis set will be analyzed. Data for this secondary endpoint will be analyzed via a repeated measures ANOVA comparing mean changes in participant's total GSE-SF scores from baseline (Visit 2) to each of the 4-week treatment periods (Visit 3, 4, and 5). Significant changes will be followed up using within groups, repeated measures *t*-tests as needed.

#### **4.3.8. Change in Brief Measure of Worry Severity (BMWS) Scores from Baseline to Each 4-Week Treatment Period**

##### **4.3.8.1. Definition of Endpoint**

The Brief Measure of Worry Severity (BMWS) is an 8-item, self-administered questionnaire that measures various components of dysfunctional worry. The BMWS total score is derived from the summation of all eight questions. Answer options for the BMWS are coded as: 0 = *Not true at all*, 1 = *Somewhat true*, 2 = *Moderately true*, 3 = *Definitely true*. The range of total BMWS score is 0 to 24 (with higher scores indicating more worry within the participant).

##### **4.3.8.2. Main Analytical Approach**

See Appendix 6.3.6 for BMWS scoring information. Only data from those participants who meet criteria for the Full Analysis set will be analyzed. Data for this secondary endpoint will be analyzed via a repeated measures ANOVA, comparing mean changes in participant's total BMWS scores from baseline (Visit 2) to each of the 4-week treatment periods (Visit 3, 4, and 5). Significant changes will be followed up using within groups, repeated measures *t*-tests as needed.

### **4.4. Exploratory Endpoint Analysis**

Data for each of the exploratory outcome measures will be statistically analyzed for within group changes comparing baseline (Visit 2) to each of the 4-week treatment periods (Visit 3, 4, and 5). via a repeated measures analysis of variance (ANOVA) and/or dependent *t*-tests tests as appropriate, as well as bivariate correlations.

#### **4.4.1. Change in Activity and Sleep from Baseline to Each 4-Week Treatment Period**

##### **4.4.1.1. Definition of Endpoint**

The variables used to measure change in activity and sleep will be derived from participant's activity tracker they are to wear and sync daily. The participants' data are collected throughout

This document, including any source code, is the property of [Clinvest Research LLC](https://www.clinvestresearch.com), and may contain proprietary, confidential, or legally privileged information. No part of this report, or any information contained therein, may be disseminated without the written consent of [Clinvest Research LLC](https://www.clinvestresearch.com).

the course of the study. The data are synced on their app from the activity tracker and all information is then sent to Fitabase (<https://www.fitabase.com>).

- **Activity** will be defined by totaling the participants steps **[Steps]** from each day per treatment period.
- **Sleep** will be defined by totaling the participant's seconds of sleep **[DeepSleepDurationInSeconds] + [LightSleepDurationInSeconds]** from each day per treatment period. Sleep seconds will be converted to minutes for reporting purposes.

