4.1. Overall Design

This is a multicenter, open label study assessing the interictal impact of erenumab-aooe in participants with migraine. The study population will consist of 54 participants 18 to 65 years old, with at least 4 and up to 20 migraine days per month (inclusive) following ICHD-III criteria for migraine with or without aura.

At Visit 1, the participant will sign the informed consent indicating they are willing to participate in the study and will provide basic demographic information, have a comprehensive review of their medical history and prior and concomitant medications. A physical and neurological examination (including vital signs) will be performed as well as a 12-lead Electrocardiography (ECG), screening CMP labs, and the PHQ-9 will be completed. Women of childbearing potential (WOCB) will complete a urine pregnancy test. All participants will complete the MFIQ questionnaire. Inclusion and Exclusion criteria will also be reviewed. Participants who meet the study criteria will be dispensed the activity tracker and its associated phone application instructions, as well as their unique Daily Headache Diary (DHD) URL and its instructions. Participants will then enter into a 28-day run-in period. During the 28-day run-in period, all participants will be monitored through the use of electronic Daily Headache Diary (DHD) to ensure they continue to meet all inclusion criteria, and none of the exclusion criteria. During this run-in period, participants will continue treating their migraines and other defined conditions with their usual treatment providing it has been stable for a minimum of 3 months. Daily electronic diaries will be used to assess symptoms and treatment response throughout the run-in period.

Visit 2 will take place 28 to 33 days following Visit 1. Those participants who (1) continue to meet eligibility criteria (2) experienced 4-20 migraine days that meet ICHD-III criteria for migraine and (3) have completed at least 23/28 diary days will be eligible to be enrolled into the study. At this visit a physical examination (including vital signs) will be performed, WOCB will complete a urine pregnancy test, and all participants will complete the PHQ-9. Medical history and/or adverse events and concomitant medications will be reviewed and updated as needed. Participant's DHD will be reviewed for compliance, and participants will complete the following questionnaires:

- MFIQ
- MIBS-4
- WPAI-M

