#### 4.1.1. Missing Data

Missing data for full analysis population participants will be imputed as follows:

- Missing values on questionnaire items will be handled according to the questionnaire's scoring manual. When no guidance is specified in a questionnaire scoring manual, missing items will be left null and the score and/or sub-score will be imputed using a last observation carried forward (LOCF) method. This type of imputation replaces the missing value with the last observation value obtained for the participant.
- Missing DHD entries (Monthly Migraine Days) will be imputed as follows:
  - < 14 DHDs completed: Participant's average MMDs for that study period will be replaced with their last study period's MMD using the LOCF method.
  - $\geq 14$  DHDs completed: Participant's average MMDs for that study period will be imputed based on the data available in that study period and prorated to 28 days.
- Missing Garmin data (Steps and Sleep) will be imputed as follows:
  - < 14 days synced: Participant's average steps and/or sleep for that study period will be replaced with their last study period's steps and/or sleep using the LOCF method.
  - $\geq 14$  days synced: Participant's steps and/or sleep for the missing day will be imputed using the participant's mean steps and/or sleep for the data available in that study period.

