#### 4.3.4. Change in Migraine Days from Baseline to Each 4-Week Treatment Period

##### 4.3.4.1. Definition of Endpoint

Headache and Migraine data will be recorded by the participants into an electronic daily headache diary (DHD) throughout the study. The DHDs are web-based and can be completed on any internet enabled device using the participant's unique log in credentials. Site personnel will be responsible for instructing participants on the requirement for timely and daily completion of the DHD.

Clinic visits are to occur every 28 days throughout the study; however, in practice, there may or may not be an exact 28-day duration between two consecutive visits. As such, participants may have more or less than 28 diary entries between two consecutive visits. To account for this, the following will be utilized:

- **Baseline:** eDiary information entered during the *last* 28 continuous days of the run-in period will serve as the “baseline” for calculating change from baseline. For example, if a participant's run-in period is 31 days long, and the participant entered eDiary information for all 31 days, the last 28 days (leading up to first drug administration) will be used to calculate and derive endpoint variables, with the first three eDiary entries (days 1, 2, and 3) being discarded from the analysis datasets.
- **Treatment Months:** If a participant enters more than 28 days of eDiary information between clinic visits during the treatment phase of the study, the *first* 28 continuous day's eDiary entries for each period/month will be used for analyses. For example, if a participant has a duration of 31 days between Visit 2 and Visit 3, and the participant entered eDiary information for all 31 days, the first 28 days (following Visit 2) of eDiary information will be used to calculate and derive endpoint variables, with the last three eDiary entries (days 29, 30, and 31) being discarded from the analysis datasets.

Migraine headache days are defined in this study as an attack within a calendar day (00:00 to 23:59) that meet at least one of the two following criteria:

1. A headache attack that includes all of the following criteria:

This document, including any source code, is the property of [Clinvest Research LLC](#), and may contain proprietary, confidential, or legally privileged information. No part of this report, or any information contained therein, may be disseminated without the written consent of [Clinvest Research LLC](#).

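### Tracker activity and sleep are defined as period totals with no fixed number of days, so period length alone can look like a change from baseline

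*SAP*

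**What the plan says.** SAP section 4.4.1.1 states that activity "will be defined by totaling the participants steps" "from each day per treatment period". Sleep is the sum of deep and light sleep seconds over the same days. Neither definition divides by a number of days or says which days make up a period.

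SAP section 4.1.1 describes tracker data differently. With fewer than 14 synced days, the participant's "average steps and/or sleep for that study period will be replaced" by the previous period's value. With 14 or more, each missing day is filled with the participant's "mean steps and/or sleep for the data available in that study period".

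SAP section 4.4 describes the exploratory comparisons as "comparing baseline (Visit 2) to each of the 4-week treatment periods (Visit 3, 4, and 5"). SAP section 4.4.1.2 adds the repeated-measures ANOVA and follow-up t-tests, but no window.

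For migraine days the SAP is explicit. Section 4.3.4.1 acknowledges that "participants may have more or less than 28 diary entries between two consecutive visits", and keeps the last 28 run-in days and the first 28 days of each treatment month. Under section 4.1.1, a diary period with at least 14 entries is "imputed based on the data available in that study period and prorated to 28 days". Both rules are written for the diary only.

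The visit schedule lets period lengths vary. Protocol section 4.1 says "Visit 2 will take place 28 to 33 days following Visit 1", and Visits 3 to 5 fall on Days 29, 57 and 85, each with a 3-day margin either way.

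**The concern.** A total grows with the number of days summed; a daily mean does not. Section 4.4.1.1 reads as a total and section 4.1.1 as an average, so two programmers could follow the SAP and analyse different quantities. The rule for 14 or more synced days does not settle the matter: filling a missing day with the period mean changes a total but leaves a mean as it was. Nor does filling remove the length effect, since a filled total is still the daily mean times the days in the period.

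The imbalance has a direction. The run-in can be longer than 28 days but not shorter, while treatment months centre on 28. Untrimmed totals would therefore, on average, show a false fall in activity and sleep whenever run-ins exceed 28 days. The protocol's background section hypothesises improvement in daily activity, so the main risk is that a real gain is masked or that no change is reported as a decline. Variation in single periods also adds noise to the ANOVA.

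**Working it through.** The plan states no figure for the tracker endpoints, so there is none to reproduce. The only computed design figure is the primary endpoint's sample size of 54. It reproduces (paired t-test, d = 0.50, two-sided alpha 0.05: power 0.950 at n = 54) and is not affected by this point.

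**Period lengths**, from the visit windows in Protocol section 4.1 and the Schedule of Activities, with Visit 2 as Day 1:

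- Run-in: 28 to 33 days.
- Month 1 (Visit 2 to 3): 28 ± 3 = 25 to 31 days.
- Months 2 and 3 (between two visits that each have a ± 3-day margin): 28 ± 6 = 22 to 34 days.
- Visit 2 to Visit 5: 84 ± 3 = 81 to 87 days, or 27 to 29 days per month.

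**Formula.** With constant daily values and untrimmed totals, apparent change = (treatment days ÷ run-in days) − 1.

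**28-day treatment month:**

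| Run-in (days) | Apparent change |
|---|---|
| 28 | 28/28 − 1 = 0% |
| 29 | 28/29 − 1 = −3.4% |
| 30 | 28/30 − 1 = −6.7% |
| 31 | 28/31 − 1 = −9.7% |
| 32 | 28/32 − 1 = −12.5% |
| 33 | 28/33 − 1 = −15.2% |

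**Group average.** The documents do not give actual run-in lengths, so this is a range by assumption: 0% if all are 28 days; −3.4% if uniform over 28 to 30 (mean of the first three rows); −7.9% if uniform over 28 to 33 (mean of all six); −15.2% if all are 33 days.

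**Limits for one participant:**

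- Month 1: 25/33 − 1 = −24.2% to 31/28 − 1 = +10.7%.
- Months 2 and 3: 22/33 − 1 = −33.3% to 34/28 − 1 = +21.4%.
- Average of the three months: 27/33 − 1 = −18.2% to 29/28 − 1 = +3.6%.

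**Noise with every run-in at 28 days.** Assume visit offsets are independent and uniform on the whole days −3 to +3, so each has variance 4. The mean artefact is 0%. Its SD is 2/28 = 7.1% in month 1 and √8/28 = 10.1% in months 2 and 3.

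**Illustration of test error.** A simulation applied a paired t-test to untrimmed totals with 54 participants and no true change. Its inputs are assumptions that are not in the documents: mean 7,000 steps/day, between-person lognormal SD 0.35, day-to-day CV 40%, and period-level CV of 10%, 20% or 30%. Month 1 rejection rates at two-sided 0.05 were:

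| Run-in | CV 10% | CV 20% | CV 30% |
|---|---|---|---|
| All 28 days | about 5% | about 5% | about 5% |
| Uniform 28–30 | 24% | 12% | 8% |
| Uniform 28–33 | 84% | 45% | 24% |
| All 33 days | 100% | 95% | 70% |

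With every period fixed at 28 days the rate was 4.7% to 5.3%.

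**The case against.** The best defence is that the plan repeatedly calls the treatment periods 4-week periods and calls the run-in a 28-day phase. On that reading a period total is a 28-day total, and filling missing days before totalling makes sense. Section 4.1.1 also applies the word average to monthly migraine days, which section 4.3.4.2 defines as a count, so the clash over averages may be loose wording. The tracker is dispensed at Visit 1, so the run-in is evidently its baseline, and naming Visit 2 is only a general statement covering all exploratory outcomes. Finally, the extreme single-month figures need one participant with a 33-day run-in, one visit at the late limit and the next at the early limit.

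Part of this stands. The run-in is the natural baseline and only its exact days are unstated. The extremes are limits for one person, not group effects, and the simulated error rates depend on assumed variances. The artefact also works against the hypothesised improvement, not for it.

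The labels do not close the gap. The same documents allow a run-in of up to 33 days, and section 4.3.4.1 recognises that intervals differ from 28 days and needed an explicit rule for the diary despite the same labels. Nothing extends that rule to the tracker, and section 4.4.1.1 as written sums every day in the period.

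**Conclusion.** The concern holds. The SAP does not say whether tracker activity and sleep are totals or daily averages, or which days count. If daily averages are analysed, period length has no effect. If untrimmed totals are analysed, as section 4.4.1.1 reads, an unchanged participant shows 0% to −15.2% in a 28-day treatment month. The group average depends on run-in lengths the documents do not give, and is −7.9% if they are uniform over 28 to 33 days. The percentage limits follow from the visit windows alone; the averages, SDs and rejection rates rest on the assumptions stated with them. The endpoint is exploratory, and the primary analysis and the sample size are untouched. The change should be made, but it does not threaten the main conclusion.

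**What to change.** In section 4.4.1.1, define activity as mean steps per synced day and sleep as mean minutes per synced day in each period. State the tracker baseline window, for example the last 28 days of the run-in, as for the diary. In section 4.1.1, use the same daily mean, and keep the existing rule that carries the previous period's value forward when fewer than 14 days are synced. Filling single missing days then becomes redundant, because it does not alter a mean. Trimming treatment months to their first 28 days is optional.

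A total scaled to 28 days would serve equally well. Trimming alone would not be enough for it, since treatment months can be shorter than 28 days.

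The cost is SAP wording and a simple change to the derivation, with no new data. A 28-day baseline window discards at most 33 − 28 = 5 run-in tracker days per participant.

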8.1.8. Activity and Sleep via wearable device

Participants' activity and sleep data will be recorded via a sponsor-provided wearable device (e.g., Fitbit or similar). Participants may also be required to install the wearable device's phone application on their personal phones in order for the data to be transferred to the sponsor. Site personnel will be responsible for instructing participants on the requirement(s) of the wearable device and its associated phone application if applicable.

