To evaluate the efficacy of erenumab on activity and sleep.	Change from baseline to each 4-week treatment month within subjects treated with erenumab-aooe on activity and sleep measured through a wearable device.
To evaluate the efficacy of erenumab on functional impact of migraine.	Change from baseline to each 4-week treatment month within subjects treated with erenumab-aooe on Functional Assessment of Migraine Scale (FAMS) scores.
To evaluate the correlation between the Functional Assessment of Migraine Scale (FAMS) and other migraine related Patient Reported Outcome (PRO) measures.	
Correlation between Functional Assessment of Migraine Scale (FAMS) and the following migraine related Patient Reported Outcome (PRO) measures:
 
 
• Global Migraine Functional Impact Questionnaire (MFIQ)
 
• Migraine interictal burden scale (MIBS-4)
 
• Work Productivity and Activity Impairment- Migraine (WPAI-M)
 
• Neuro-QoL Sleep Disturbance Short Form (SDSF)
 
• General Self-Efficacy Short Form (GSE-SF)
 
• Brief Measure of Worry Severity (BMWS)
 

Safety	
To evaluate the safety and tolerability of participants treated with erenumab-aooe.	Safety and tolerability of erenumab-aooe in study participants via collection of adverse events and safety evaluations.

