#### **4.4.1.2. Main Analytical Approach**

All participant files from Fitabase will be downloaded and coded according to the current version of the Fitabase Garmin Data Dictionary (Last updated version 6/4/2020 as of time of writing). Only data from those participants who meet criteria for the Full Analysis set will be analyzed. Data for this exploratory endpoint will be statistically analyzed via a repeated measures ANOVA, comparing baseline changes in activity and sleep to each of the treatment month(s) activity and sleep. Significant changes will be followed up using within groups, repeated measures *t*-tests as needed.

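### The SAP counts only deep and light sleep and does not say how REM is handled; if the tracker exports REM as a separate field, reported sleep is understated and shifts into or out of REM read as sleep lost or gained.

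*SAP*

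**What the plan says.** SAP 1.1 lists an exploratory endpoint of change from baseline to each treatment month in "activity and sleep measured through a wearable device". SAP 4.4.1.1 says that sleep "will be defined by totaling the participant's seconds of sleep" and gives one formula for it, "DeepSleepDurationInSeconds] + [LightSleepDurationInSeconds", summed over the days of each treatment period and reported in minutes. No third component is added.

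SAP 4.4.1.2 says the tracker files will be "coded according to the current version of the Fitabase Garmin Data Dictionary (Last updated version 6/4/2020 as of time of writing". That dictionary is not reproduced. Protocol 8.1.8 leaves the device open, as a "sponsor-provided wearable device (e.g., Fitbit or similar"; the SAP refers to Garmin data but names no model.

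For periods with at least 14 synced days, the rule in SAP 4.1.1 is: "Participant's steps and/or sleep for the missing day will be imputed using the participant's mean steps and/or sleep for the data available". With fewer than 14, the previous period's value is carried forward.

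REM sleep appears in neither document.

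**The concern.** The target in SAP 4.4.1.1 is the time a participant spends asleep, but the formula adds two named stages. The two agree only if every minute the device scores as sleep falls into the deep or the light field. If REM is exported as its own field, the formula treats it in the same way as time awake.

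Two consequences would follow. Reported sleep would be too low in level. A within-person move between REM and a counted stage would also appear as a change in sleep when total sleep had not changed.

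Protocol 2.2 adds the trackers to enrich the questionnaire results, and this is the study's only device-based sleep measure. A spurious gain or loss could therefore contradict, or appear to support, the self-reported sleep score (SDSF).

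**Working it through.** The plan gives no figure for this endpoint, so there is none to reproduce. The check is algebra on the stated formula, followed by illustrations on stated assumptions.

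**Inputs**
- Formula: deep plus light seconds (SAP 4.4.1.1).
- Analysis: within-person change from baseline (SAP 1.1 and 4.4.1.2).
- Period length: 28 nights, the four-week treatment month.
- Assumed, not in the documents: total sleep of 420 min per night; a separately staged REM share from 0% (no separate field) to 25%; an illustrative 15 min per night moved from light sleep to REM.

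**Formula**

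Let D, L and R be deep, light and separately exported REM time. The endpoint is S = D + L and total sleep is T = D + L + R. Hence

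- S = T − R
- change(S) = change(T) − change(R)

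**Error in level, R per night**

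| REM share | Omitted per night | Omitted per 28 nights |
|---|---|---|
| 0% | 0 min | 0 min |
| 10% | 0.10 × 420 = 42 min | 42 × 28 = 1,176 min (19.6 h) |
| 15% | 0.15 × 420 = 63 min | 63 × 28 = 1,764 min (29.4 h) |
| 25% | 0.25 × 420 = 105 min | 105 × 28 = 2,940 min (49 h) |

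**Error in the change from baseline**

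1. REM time constant: change(R) = 0, so change(S) = change(T). There is no error.
2. Deep-to-light shift of x minutes: change(S) = −x + x = 0. There is no error.
3. REM a constant share r of total sleep: change(S) = (1 − r) × change(T). The direction is kept and the size shrinks by r, for example by 15% to 25% for r between 0.15 and 0.25.
4. Light-to-REM shift of 15 min per night with T fixed: change(S) = 0 − 15 = −15 min per night, and 15 × 28 = 420 min = 7 h per 28 days reported as lost.
5. REM share up by 5 percentage points with T fixed: 0.05 × 420 = 21 min per night, and 21 × 28 = 588 min (9.8 h) per 28 days reported as lost. A fall of the same size is reported as a gain.

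**Missing-data rule**

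The rule in SAP 4.1.1 replaces whole days or whole periods with values built from the same deep-plus-light sum. It carries any omission along and cannot restore it.

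**The case against.** The strongest case against the point is that the deciding fact lies outside the documents. There is an omission only if the export holds REM separately. SAP 4.4.1.1 names exact export variables and SAP 4.4.1.2 cites a dated dictionary, which fits authors who listed every sleep-stage field available as well as it fits an oversight. This stands. A reader might infer that the plan does discard REM sleep, but the documents do not establish that.

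Three other limits also stand:
- A reader might infer that any movement between stages distorts the endpoint. It does not, because deep-light shifts cancel exactly.
- A reader might take the 29 to 49 hours per 28 days (REM share 15% to 25%) as the error in the endpoint. It is an error in level. The endpoint is a change, and a constant REM amount drops out. Nothing in the documents suggests that treatment shifts REM by 15 minutes or any other amount.
- A reader might infer from the protocol's example of a Fitbit that participants wore devices that stage sleep differently. The SAP refers only to Garmin data and a single Garmin dictionary, so mixed devices or firmware would be conjecture.

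It is also fair to say that sleep is measured at secondary level by the SDSF, so the trial's conclusion on sleep does not rest on tracker minutes.

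The gap in the text remains. From the SAP alone, a reader cannot tell whether the reported minutes are all recorded sleep or a subset of it.

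**Conclusion.** The point holds in conditional form. The definition in SAP 4.4.1.1 is complete only if the export has no separate REM field, and neither document says whether it has one.

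On the assumed 420-minute night, the understatement in level is between 0 and 105 minutes per night. In the analysed change, the error equals the change in REM time with its sign reversed. It is zero if REM time is stable or not separately recorded, and 7 hours per 28 days in the assumed case of 15 minutes per night moving from light sleep to REM. Night length, REM share and size of shift are assumptions, not trial figures.

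Severity is low. One exploratory endpoint is affected; the primary endpoint and the sample size of 54 are not.

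**What to change.** In SAP 4.4.1.1, state whether the tracker export contains a REM field.
- If it does, define sleep as deep plus light plus REM seconds, or as the device's total sleep duration excluding awake time.
- If it does not, keep the present sum and state that it is all recorded sleep.

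Apply one definition to all participants and all periods, including baseline.

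The cost is one sentence and a look at the data dictionary. If a REM field exists, it also takes one more field from files that SAP 4.4.1.2 already plans to download. No new data collection is needed, and if there is no REM field the results do not change.
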